5.1.3.2. Patients Not Eligible for the Substudy

Beginning at Week 52,

- Patients with an IGA ≥ 3 who
 - are in the baricitinib 2-mg, 1-mg, and placebo treatment groups will be automatically rerandomized at a 1:1 ratio to baricitinib 2-mg QD or baricitinib 4-mg QD.

- are in the baricitinib 4-mg treatment group will remain on 4-mg QD (see “Rescue during Period 3” Section 7.7.5.2).
- Patients with an IGA 0, 1, or 2 who
 - are in the baricitinib 4-mg or 2-mg treatment groups and who are not eligible for the substudy (i.e., have study drug interrupted at Week 52, or have received high- or ultra-high potency TCS in the previous 14 days), or are in the placebo or baricitinib 1-mg groups will continue in their current treatment group.
 - Patients who experience a worsening of symptoms of AD such that IGA increases to ≥ 3 will be rerandomized at a 1:1 ratio to baricitinib 2-mg QD or baricitinib 4-mg QD. Patients in the baricitinib 4-mg group will remain on 4-mg.

This option for rescue is only available once for each patient and will be assigned by IWRS; investigators will remain blinded to treatment assignments. The investigator may reinstate background TCS therapy (e.g., triamcinolone 0.1% cream and/or hydrocortisone 2.5% ointment), provided the patients are not currently using TCS, and may prescribe high- or ultra-high-potency TCS following the guidelines for use of rescue therapies (see Section 7.7.5).

Once a patient has an IGA ≥ 3 in Period 3, the investigator will know that a patient is on the highest dose of baricitinib that he/she will receive in the study; therefore, if AD symptoms remain unacceptable then discontinuation should be considered.

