Patients whose disease cannot be controlled by the measures described above may be rescued to systemic therapies (conventional systemics or biologics). These patients will be required to discontinue investigational product and proceed to the ETV before initiating systemic treatment. However, patients rescued to systemic therapies prior to the primary endpoint (Week 16) should be encouraged to continue with study visits and assessments through Visit 8.

7.7.5.2. Rescue during Periods 3 and 4: from Week 52 (Visit 14) to Week 200 (Visit 28)

In Period 3, all patients will continue to use concomitant background TCS (e.g., triamcinolone 0.1% cream and hydrocortisone 2.5% ointment) as described in Section 7.7. In Period 4, use of concomitant may continue as directed by the investigator, as per clinical practice. All patients may be rescued at any time with high- or ultra-high-potency TCS or phototherapy as described in Section 7.7.

As mentioned in Sections 5.1.3 and 5.1.4, patients who reach an IGA ≥ 3 after entry into the randomized downtitration substudy will be automatically retreated with their presubstudy dose of baricitinib.

Patients not eligible for the substudy and who present with an IGA ≥ 3 at Week 52 or anytime thereafter will automatically be rerandomized at a 1:1 ratio to baricitinib 2-mg QD or baricitinib 4-mg QD, but this will only occur once. Patients randomized to baricitinib 4-mg QD at baseline (Week 0, Visit 2) will stay on this dose for the remainder of the trial regardless of IGA.

Patients whose disease cannot be controlled by the measures described above may be rescued to systemic therapies (conventional systemics or biologics). Whenever possible during this Period, it is recommended to wait for at least 4 weeks after the visit at which the patient has reached IGA ≥ 3 to initiate rescue with systemic therapies.

Patients rescued with high- or ultra-high-potency TCS will continue to take investigational product and use of topical rescue therapy will be documented in the eCRF.

Patients rescued with phototherapy will remain in the trial and will be required to temporarily interrupt the use of investigational product until completion of the phototherapy.

Patients who need rescue with systemic therapies (conventional systemics or biologics) during Period 3 will be required to discontinue investigational product and to proceed to the ETV before initiating systemic treatment.

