All Patients Entering the Substudy To evaluate the change in clinical response after treatment downtitration from baricitinib	
 
• 4-mg to 2-mg compared with patients who are rerandomized to remain on baricitinib 4-mg
 
• 2-mg to 1-mg compared with patients randomized to remain on baricitinib 2-mg
 

Patients Entering the Substudy with IGA 0 or 1 To evaluate the change in clinical response after treatment downtitration from baricitinib	
 
• 4-mg to 2-mg compared with patients who are rerandomized to remain on baricitinib 4-mg
 
• 2-mg to 1-mg compared with patients randomized to remain on baricitinib 2-mg
 

Patients Retreated during Substudy To evaluate the ability to recapture efficacy based on clinical measures after experiencing a loss of treatment benefit:	
 
• Proportion of patients with a response of IGA 0, 1, or 2 within 16 weeks of retreatment
 
• Proportion of patients with a response of IGA 0 or 1 within 16 weeks of retreatment
 
• Proportion of patients with a response of EASI75 from baseline of originating study within 16 weeks of retreatment
 

Patients Not Entered into Substudy These are prespecified objectives that will not be adjusted for multiplicity	
All Patients To evaluate the long-term effect of baricitinib dose on clinical measures	
 
• Proportion of patients with a response of IGA 0, 1, or 2 assessed at Weeks 68 and 104
 
• Proportion of patients with a response of IGA 0 or 1 assessed at Weeks 68 and 104
 
• Proportion of patients with a response of EASI75 assessed at Weeks 68 and 104
 

Patients with IGA 0 or 1 To evaluate the long-term effect of baricitinib dose on clinical measures	
Non-responder Patients at Week 52	

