d At Visit 2 (W0) and up to Visit 22 (W104), patients will be supplied with mild- and moderate-potency TCS to be applied per the guidelines in Section 7.7.2 in the study protocol.

e At Week 52, responders (IGA 0 or 1) and partial responders (IGA 2) who were assigned to baricitinib 4-mg or 2-mg, at randomization, are currently receiving investigational product (does not currently have study drug interrupted), and have not used high- or ultra-high-potency TCS in the previous 14 days will be enrolled into the downtitration substudy. If a patient in the substudy has an IGA ≥3 during Periods 3 or 4, they will be retreated automatically with their presubstudy baricitinib dose for the remainder of the study.

f At Week 52, responders (IGA 0 or 1) and partial responders (IGA 2) in the baricitinib 4-mg or baricitinib 2-mg treatment groups who are not eligible for the randomized downtitration substudy and those who are in the baricitinib 1-mg or placebo groups will remain on their current dose of investigational product. If worsening of AD symptoms occurs any time during Periods 3 or 4 such that a patient's IGA is  $\geq 3$ , with the exception of patients in the baricitinib 4-mg group, they will be rerandomized automatically at a 1:1 ratio to baricitinib 2-mg QD or baricitinib 4-mg QD. Rerandomization will only occur once. Patients in the baricitinib 4-mg group will remain on 4-mg.

g Beginning at Visit 14 (Week 52), nonresponders (IGA  $\geq 3$ ) in the placebo, baricitinib 1-mg or baricitinib 2-mg treatment groups will be rerandomized at a 1:1 ratio to baricitinib 4-mg or baricitinib 2-mg QD. Nonresponders randomized to baricitinib 4-mg at baseline will remain on 4-mg. After rerandomization, patients will remain on the same dose of baricitinib for the remainder of the study.

h Occurs approximately 28 days after the last dose of IP. Not required for patients who have been off drug for 28 days or more at the time of their last visit.

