**Table JAIN.6.3. Treatment Groups and Comparisons for the 104-Week Interim and Final DBL Analysis Population**

Study Period	Analysis Population	Treatment Group	Abbreviation	Analyses Category
Long-Term Extension Period (Period 3 and Period 4)	LTE Substudy Population	Bari 4-mg in Period 2, were re-randomized to (Bari 4-mg or Bari 2-mg) in Period 3/Period 4;	Bari 4-mg/4-mg Bari 4-mg/2-mg	Efficacy
	LTE Substudy Population with IGA(0,1) at Week 52	Bari 2-mg in Period 2, were re-randomized to (Bari 2-mg or Bari 1-mg) in Period 3/Period 4.	Bari 2-mg/2-mg Bari 2-mg/1-mg	Efficacy for Subsetting IGA(0,1) at Week 52
	LTE Substudy Relapse Population	Bari 4-mg in Period 2, were re-randomized to (Bari 4-mg or Bari 2-mg) in Period 3/Period 4, retreated with presubstudy of Bari 4-mg when Relapse occurred;  Bari 2-mg in Period 2, were re-randomized to (Bari 2-mg or Bari 1-mg) in Period 3/Period 4, retreated with presubstudy of Bari 2-mg when Relapse occurred.	Bari 4-mg/4-mg/4-mg Bari 4-mg/2-mg/4-mg  Bari 2-mg/2-mg/2-mg Bari 2-mg/1-mg/2-mg	Time to Relapse
	LTE Non-responder Population	Bari 4-mg stays Bari 4-mg in Period 2 & Period 3/Period 4;	Bari 4-mg Bari 2-mg /2-mg Bari 2-mg/4-mg Bari 1-mg/2-mg Bari 1-mg/4-mg PBO/Bari 2-mg PBO/Bari 4-mg	Efficacy

	(Bari 2-mg, Bari 1-mg or Placebo) were re-randomized to (Bari 2-mg or Bari 4-mg) in Period 3.		
Long-Term Extension (LTE) Responders & Partial Responders who did not enter the Substudy	Bari 4-mg, Bari 2-mg Bari 1-mg, Placebo will continue on the same treatment	Bari 4-mg Bari 2-mg Bari 1-mg Placebo	Efficacy
Safety Population	Bari 4-mg, Bari 2-mg Bari 1-mg, Placebo who continuously got treated from baseline and censored in case of dose change.	Bari 4-mg Bari 2-mg Bari 1-mg Placebo All Bari	Safety

Abbreviations: Bari = baricitinib; IGA = Investigator's Global Assessment for AD; LTE = Long-Term Extension; PBO = placebo.

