For **Long-Term Extension(LTE) Substudy analysis**, the censoring rule will censor the efficacy and health outcome results after permanent study drug discontinuation or after the retreatment, whichever occurred first.

For **Long-Term Extension(LTE) Non-responder analysis** the censoring rule will censor the efficacy and health outcome results after permanent study drug discontinuation.

For **Time to Relapse analysis**, if Relapse (IGA $\geq 3$  in Period 3 or Period 4) occurred on or after permanent study drug discontinuation, the event would be censored on the last available visit date.

For **Long-Term Extension (LTE) Responders & Partial Responders who did not enter the Substudy** the censoring rule will censor the efficacy and health outcome results after permanent study drug discontinuation or after the dose change, whichever occurred first.

Nonresponder imputation (for categorical variables) and MMRM (for continuous variables) will be the primary methods used to handle missing data. Sections 6.3.1 through 6.3.5 summarize the imputation methods for the various efficacy and health outcome endpoints.

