### **6.3.3. Modified Last Observation Carried Forward**

A modified last observation analysis is performed by carrying forward the last postbaseline assessment for the continuous measures, assuming that effects of treatments remain the same after the occurrence of the intercurrent event (after application of the primary censoring rule). After mLOCF imputation, data from patients with non-missing baseline and at least 1 postbaseline observation will be included in the analyses. These mLOCF analyses help ensure that the maximum number of randomized patients who were assessed postbaseline will be included in the analyses.

For patients who experience any intercurrent event at any time, the last non-missing postbaseline observation on or prior to this event will be carried forward to subsequent time points for evaluation. If a patient does not have a non-missing observed record (or one imputed by other means) for a postbaseline visit prior to discontinuation or rescue, the last postbaseline record prior to the missed visit will be used for the visit.

For patients who entered the Period 3 and Period 4 treatment, the mLOCF in Period 3 and Period 4 will be performed by carrying forward the last available assessment if the treatment dosage did not change at the time of the last available assessment, which could be the assessment in Period 2, Period 3, or Period 4. If a patient was re-randomized at Week 52 and the treatment dosage

changed on/after Week 52, the mLOCF will be performed by carrying forward the last available assessment after the dosage change (Week 52), and before the censoring rule's cut-off date. The observed values after the censoring rule's cut-off date (i.e., retreatment such as dose up-titrated back to presubstudy dose) will not be carried forward. If Week 52's value is used as the Baseline, then the post-baseline (after Week 52) value could be carried forward to subsequent time points for evaluation.

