**Table JAIN.6.9. Description of Primary, Secondary, and Exploratory Efficacy Analyses (Period 3 and Period 4)**

Measure	Variable	Population (Section 6.2.1)	Analysis Method (Section 6.2.2)	Time Point	Baseline definition
Validated Investigator's Global Assessment for AD (IGA)	Proportion of patients with a response of IGA 0 or 1	LTE Substudy Population	Descriptive using Obs and mLOCF	Weeks 52-200	N.A.
		LTE Substudy Population – Patients with IGA of 0 or 1 at Week 52	Descriptive using Obs and mLOCF	Weeks 52-200	
		LTE Non-responder Population	Descriptive using Obs and mLOCF	Weeks 52-200	
	Proportion of patients with a response of IGA 0, 1, or 2	LTE Responder & Partial Responders who did not enter the substudy	Descriptive using Obs and mLOCF	Weeks 52-200	
	Time to relapse (time to IGA $\geq 3$ )	LTE Substudy Relapse Population	
 
Descriptive
 
Kaplan-Meier plot
 
	Downtitration and withdrawal period	N.A.
	Proportion of patients with a response of IGA(0, 1), IGA(0, 1, 2) within 16 weeks of Disease Retreatment	LTE Substudy Relapse Population	Descriptive	Downtitration and withdrawal period	N.A.
Eczema Area and Severity Index (EASI)	Proportion of patients achieving EASI75 (achieving EASI percent change from baseline $\leq -75$ )	LTE Substudy Population	Descriptive using Obs and mLOCF	Weeks 52-200	Week 0 Baseline
		LTE Substudy Population - Patients with IGA of 0 or 1 at Week 52	Descriptive using Obs and mLOCF	Weeks 52-200	Week 0 Baseline
		LTE Non-responder Population	Descriptive using Obs and mLOCF	Weeks 52-200	Week 0 Baseline

Measure	Variable	Population (Section 6.2.1)	Analysis Method (Section 6.2.2)	Time Point	Baseline definition
	Proportion of patients achieving EASI50	LTE Responder & Partial Responders who did not enter the substudy	Descriptive using Obs and mLOCF	Weeks 52-200	Week 0 Baseline
	Proportion of patients achieving EASI90				
Eczema Area and Severity Index (EASI)	Change from baseline in EASI score	LTE Substudy Population	Descriptive using Obs and mLOCF	Weeks 52-200	Week 0 Baseline
	Percent change from baseline in EASI score	LTE Substudy Population – Patients with IGA of 0 or 1 at Week 52	Descriptive using Obs and mLOCF	Weeks 52-200	Week 0 Baseline
		LTE Non-responder Population	Descriptive using Obs and mLOCF	Weeks 52-200	Week 0 Baseline
		LTE Responder & Partial Responders who did not enter the substudy	Descriptive using Obs and mLOCF	Weeks 52-200	Week 0 Baseline

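### For Week 52 responders outside the substudy, censoring at dose change depends on the arm, so the descriptive by-dose tables can show an artificial dose trend

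*SAP*

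**What the plan says.** The objective for patients not entered into the substudy (SAP 4.2.2) is "To evaluate the long-term effect of baricitinib dose on clinical measures", with IGA and EASI75 response at Weeks 68 and 104. Table JAIN.6.3 sets 4-mg, 2-mg, 1-mg and placebo side by side for responders and partial responders outside the substudy, and describes the groups as staying on their treatment: "Bari 1-mg, Placebo will continue on the same treatment". Table JAIN.6.9 gives the method as "Descriptive using Obs and mLOCF".

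SAP 6.3 censors this population's efficacy and health outcome data "after permanent study drug discontinuation or after the dose change, whichever occurred first".

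The dose change follows from the design. When IGA reaches 3 or more, SAP Section 5 says of all but the 4-mg group: "they will be rerandomized automatically at a 1:1 ratio to baricitinib 2-mg QD or baricitinib 4-mg QD. Rerandomization will only occur once". For 4-mg, Protocol 5.1.3.2 says "Patients in the baricitinib 4-mg group will remain on 4-mg", and Protocol 7.7.5.2 says such patients "will stay on this dose for the remainder of the trial regardless of IGA".

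For Periods 3 and 4, SAP 6.3.3 defines mLOCF as "carrying forward the last available assessment if the treatment dosage did not change at the time of the last available assessment", and does not carry forward values observed after the cut-off.

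**The concern.** The censoring event is the dose change, not the relapse, and the same relapse leads to a dose change with a probability that depends on the arm: 1 on placebo and 1-mg, about 0.5 on 2-mg, 0 on 4-mg.

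The two displays then treat identical patients differently. Under mLOCF, a relapse on placebo or 1-mg stays a failure at every later visit, while a 4-mg patient who relapses continues to be scored and can count as a responder again. Under observed data, placebo and 1-mg relapsers leave the denominator after the relapse visit, while 4-mg relapsers stay in it.

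The SAP's other two extension rules do not have this feature. The substudy rule cuts at retreatment, which Table JAIN.6.3 applies also to arms that kept their dose (4-mg/4-mg/4-mg and 2-mg/2-mg/2-mg). The nonresponder rule cuts only at permanent discontinuation.

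At stake is the reading of tables whose stated purpose is the long-term effect of dose.

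**Working it through.** The plan states no figure on this point, so there is none to reproduce. The check asks what the tables would show if the disease course were the same in every arm.

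**Inputs from the documents.** Probability that a first relapse causes a dose change: c = 1 (placebo, 1-mg), 0.5 (2-mg), 0 (4-mg), from Protocol 5.1.3.2 and 7.7.5.2 and SAP Section 5. Visits after Week 52 (Schedule of Activities): Weeks 56, 60, 64, 68, 76, 84, 92, 104, so n = 4 at Week 68 and n = 8 at Week 104.

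**Assumptions.** Relapse probability r and recovery probability q per visit, equal in all arms (the documents give neither); everyone starts at IGA 0-2; no permanent discontinuation; 2-mg re-randomised to 2-mg is no dose change; the censoring rule applies to both displays; the IGA ≥3 value that triggers the switch is the last one kept. SAP 6.3.3 carries forward the last value on or before the intercurrent event, which supports the last assumption. If that value were dropped, the earlier responder value would be carried instead; the direction would change but the asymmetry would remain.

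**Formulas** (proportion with IGA 0, 1 or 2 at visit n)
- 4-mg, both displays: q/(r+q) + [r/(r+q)] × (1−r−q)^n
- Placebo and 1-mg, mLOCF: (1−r)^n
- Placebo and 1-mg, observed: (1−r)^n / (1−r)^(n−1) = 1−r
- 2-mg, mLOCF: the mean of the placebo and 4-mg mLOCF values
- 2-mg, observed: that mean divided by 1 − 0.5 × [1 − (1−r)^(n−1)]

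**Worked case, r = 0.10, q = 0.30, Week 104**
- 4-mg: 0.75 + 0.25 × 0.6^8 = 75.4%
- Placebo and 1-mg, mLOCF: 0.9^8 = 43.0%; observed: 90.0%
- 2-mg, mLOCF: (43.0 + 75.4)/2 = 59.2%; observed: 0.592 / (1 − 0.5 × 0.522) = 80.1%
- Already censored: placebo and 1-mg 1 − 0.9^7 = 52.2%; 2-mg 26.1%; 4-mg 0%

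At Week 68 the same inputs give 65.6 / 71.9 / 78.2% (mLOCF) and 90.0 / 83.2 / 78.2% (observed) for placebo and 1-mg / 2-mg / 4-mg.

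**Range at Week 104** (gap = 4-mg minus placebo, in points)

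| r | q | Placebo mLOCF | Placebo observed | 4-mg (both) | mLOCF gap | Observed gap |
|---|---|---|---|---|---|---|
| 0.05 | 0.10 | 66.3 | 95.0 | 75.7 | +9.4 | -19.3 |
| 0.10 | 0 | 43.0 | 90.0 | 43.0 | 0 | -47.0 |
| 0.10 | 0.10 | 43.0 | 90.0 | 58.4 | +15.4 | -31.6 |
| 0.10 | 0.30 | 43.0 | 90.0 | 75.4 | +32.4 | -14.6 |
| 0.10 | 0.50 | 43.0 | 90.0 | 83.3 | +40.3 | -6.7 |
| 0.15 | 0.50 | 27.2 | 85.0 | 76.9 | +49.7 | -8.1 |

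The observed gap is about -7 to -32 points at 10% relapse. The same formulas widen it to about -4 (r = 0.05, q = 0.50: 90.9 − 95.0) and -39 (r = 0.15, q = 0.10: 46.0 − 85.0) over the whole grid with recovery of 10-50%.

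**Discontinuation on 4-mg.** With r = 0.10, q = 0.40 and none, 4-mg mLOCF is 80% against 43% on placebo, a gap of 37 points. An assumed 20% discontinuation per relapsed visit lowers 4-mg to 67% (gap 24), and 50% lowers it to 54% (gap 11).

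**With one cut-off in all arms.** Cutting at the first IGA ≥3 everywhere gives (1−r)^n in every arm: at r = 0.10, 65.6% at Week 68 and 43.0% at Week 104.

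**The case against.** Censoring at dose change is a defensible on-assigned-dose choice. Placebo data after a switch to 2-mg or 4-mg are not placebo data, whereas 4-mg data after a relapse are still 4-mg data. A common cut-off at first relapse would score a 4-mg patient with IGA 0 or 1 at Week 104 as a failure because of an earlier relapse, which answers a different question from response at the visit. This stands, and is why the common cut-off should be added to the planned displays rather than replace them.

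A reader might infer that no 4-mg patient is ever censored. The documents do not support that: the same rule censors at permanent discontinuation, Protocol 5.1.3.2 says discontinuation should be considered if symptoms remain unacceptable after IGA ≥3, and Protocol 7.7.5.2 requires it for systemic rescue in Period 3. This narrows the mLOCF gap.

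A reader might also infer that the two displays must give opposite trends. The mLOCF trend needs some 4-mg relapses to recover; with none, only the observed-data trend remains.

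The groups also differ by selection. Responders on 4-mg and 2-mg are here only because study drug was interrupted at Week 52 or high- or ultra-high-potency TCS was used in the previous 14 days; all placebo and 1-mg responders are here by design. An identical disease course is therefore a device for isolating the artefact, not a forecast, and no censoring rule makes this a randomised dose comparison. That limits what the tables can show, but does not justify adding an avoidable distortion.

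Finally, SAP 6.2.2.3 makes Period 3 and 4 analyses descriptive, and SAP 6.2.2 calls efficacy beyond Week 104 exploratory, on observed data (Table JAIN.6.9 lists mLOCF to Week 200 as well). On the narrower reading, the observed-data artefact stands alone after Week 104.

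**Conclusion.** The concern holds as a reporting problem. The arm-specific dose-change limb follows from the documents and needs no assumption; the size does. With equal courses in all arms, 5-15% relapse and 10-50% recovery per visit, and no 4-mg discontinuation, the Week 104 gap (4-mg minus placebo) is about +9 to +50 points under mLOCF. Under observed data at 10% relapse it is about -7 to -32 points. With no recovery the mLOCF gap is zero. In every scenario run with relapse, at least one planned display shows a trend that dose did not cause. The 2-mg figures are intermediate if re-randomisation to the same dose is not a dose change.

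A reader might infer a type I error problem or a threat to the primary conclusion. Neither follows: these tables carry no test and lie outside the multiplicity scheme. The risk is that readers take the tables as evidence on dose.

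**What to change.** In SAP 6.3, add for this population an analysis with one cut-off in all four arms: the first IGA ≥3 visit after Week 52, or permanent discontinuation if earlier, whether or not the dose then changes.

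- Categorical endpoints: nonresponder from that visit, with all patients in the denominator.
- Continuous endpoints: carry forward the value at that visit in all arms.
- Base any by-dose reading on this display, state the selection into the groups beside it, and label the dose-change-censored observed and mLOCF tables as not comparable across doses.
- Report, by arm, the number censored by dose change and by discontinuation.
- Show responses after relapse separately by dose actually taken, including 4-mg continued and 2-mg re-randomised to 2-mg.
- Add this population's rules to footnote c of Table JAIN.6.4, which names only the substudy and nonresponder rules, and list the added display in Tables JAIN.6.9 and JAIN.6.12.

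Cost: extra programming and table entries; no new data and no change to patient management. The added display measures sustained response rather than response at the visit, and the 4-mg rate will look less favourable there than under the planned mLOCF. Selection into the groups remains.
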